4.3 Examination of subgroups

Subgroup analyses will be conducted as stated in the exploratory analyses section. It should be noted that the study was not designed to detect treatment differences with high statistical power within subgroups.

The following subgroups will be assessed and are classified as follows:

- Subjects with any triptan use within three months of screening.
- Subjects that dosed a migraine greater than 4 hours after migraine start.
- Subjects with either Topamax or Propranolol use while on study.
- Subjects with Topamax use while on study.
- Subjects with Propranolol use while on study.
- Subjects with one or more cardiovascular risk factors (CVRF)
- Subjects with treatment emergent adverse events (TEAE) of dizziness

5 GENERAL SPECIFICATIONS

This section details the specifications for summarizing all efficacy and safety endpoints.

Continuous variables will be summarized using descriptive statistics, i.e. n (number of subjects with available data), mean, median, standard deviation, minimum, and maximum. For those measures that are analyzed using change from baseline scores, descriptive statistics will also be presented on observed scores, unless otherwise noted.

Minimum and maximum values will be presented to the same precision as the raw data. Mean and median will be presented to one more decimal place than the raw data. Standard deviation will be

presented to two more decimal places than the raw data. P-values will be presented to three decimal places.

Categorical variables will be summarized using counts and percentages. Unless otherwise specified, percentages will be calculated using the numbers of subjects in the summarized population in each treatment group as denominators. Percentages will be presented with a precision of 1 digit after the decimal.

In this study, subject will enter the efficacy data on dosing and post-dose assessments in an e-diary. The e-diary records the date and time of the first dose and of the second dose and is programmed to assess specific time points and assessments as defined in the protocol based on the timing of the dose as recorded. This data is collected in the e-diary when e-diary is in migraine mode. Specifics of Migraine Mode are as below:

- Migraine Mode – First Dose
 - The e-diary enters Migraine Mode **ONLY** if the subject indicates taking his/her first dose of study medication
 - Post Dose Assessments will be completed using the Migraine Questions button at specific time intervals for up to 48 hours after the subject confirms taking study medication
 - The time intervals are 30 minutes, 1 hour, 1.5 hours, 2 hours, 3 hours, 4 hours, 24 hours, and 48 hours after the first dose of study medication. The e-diary sets the post dose assessments based on the recorded time of dosing. A subject that begins reporting their migraine at the exact time of dosing will have all of the post dose assessment time points available to them. If a subject starts recording their information in the e-diary after they dose including the time of dosing, the assessments that become available for them are based on the time of dosing, relative to when they accessed the e-diary. For example, if at 1-hour post actual dosing the subject initiates migraine mode and begins entering data into the e-diary, the subject will be allowed to respond to the initial questions about their migraine and time of dosing and then based on the time they record for dosing they automatically will miss subsequent time points, i.e.; the 30 minute and 1-hour time points. A missed time point is missed.
 - Alarms occur at the predefined time points to remind the subject it is time to complete the assessments. The Migraine Questions button is always available, but the subject is not be able to answer the questions until prompted by an alarm within a study migraine.
- Migraine Mode – Second Dose (Optional)
 - The subject should only take a second dose of study medication if the migraine pain is not gone by two hours after the first dose or the migraine pain was gone and came back two hours or more after the first dose (up to 24 hours after first dose).
 - The Dose 2 button will appear AFTER the e-diary recognizes 2 hours have passed since the first dose and remains until the 24-hour time point.
 - During the 2-hour post dose assessment the subject will be asked to indicate if he/she would like to take a second dose of study medication
 - If a second dose is reported alarm intervals are the same as for the reporting of the first dose and any remaining alarms from the first dose are cancelled. However, if

the subject inadvertently enters a dosing time of the second dose occurring prior to the first dose the first dose alarms do not stop and subject can therefore response to post-dose assessments based on time of dosing of first dose, therefore not really assessing their response to the second dose.

In the event that e-diary dates and times are not entered by subject as described in specifics of Migraine Mode but subject actually takes a dose, the dates and times for first and second dose based on subject report will be recorded in the CRF at the site when subject comes to site at Visit 2 /End of Study (EoS). Subject will be asked about their dosing and any unusual symptoms they experienced with their migraine that they had not experienced before. To make the use of CRF date entry consistent across all subjects, these CRF dates and times data will be completed for all subjects even if subject has entered the dates and times on e-diary. This may cause more validation for efficacy and safety analysis dates and times and will be further described in detail in below sections.

Observations collected prior to first dose will serve to determine a baseline measurement; the latest available measurement prior to first dose will be used as the baseline. For safety purposes, the first recorded date and time at which a dose was taken will be used for baseline, without regard for the source of that date (e-diary or CRF). For efficacy purposes, baseline values will be the Hour-0 assessment times identified in the e-diary. Analyses of efficacy data collected after the second dose may require a second "Hour-0" defined by the e-diary relative to the entered time of that second dose.

The start and end of treatment exposure for efficacy and safety analysis will always be identified from the first and last dates of dosing entered in the e-diary, when available and appear to be analysis useful data. As mentioned before if cases like those described in detailed Scenarios #4, #5 and #7 in Section 5.4 leave e-diary dates missing, alternatives from the CRF data will be used for first and second dose dates for safety analysis if there is a confirmation of dosing in the CRF. In some cases if e-diary dates appear to be out of order (CRF dates are clear legitimate corrections of e-diary for first dose and second dose), i.e.: second dose date and/or time recorded in e-diary is before first dose date and/or time; same first and second dose dates and time in e-diary, such dates and/or time will be corrected by CRF data as provided by the subject at Visit 2/EoS. These will be the exceptions where CRF dates will be considered for safety analysis. Otherwise, if the CRF dates and e-diary dates do not match, then for overall treatment exposure, earliest date available from CRF or e-diary will be considered for start of exposure and latest date available from CRF or e-diary will be considered for end of exposure. Additionally, for first dose exposure, earliest date available from CRF or e-diary will be considered for start of exposure of first dose and latest date will be considered for end of exposure of first dose. Similarly, for second dose exposure, earliest date available from CRF or e-diary will be considered for start of exposure of second dose and latest date will be considered for end of exposure of second dose. If the first dose date is missing from the e-diary data as well as CRF data but CRF has a confirmation of first dose, the eligibility-confirmation date will be used as the first alternative for safety analyses, and the randomization date will be the second alternative for safety analyses. If the confirmation of second dose is available on CRF but the second-dose date is missing in e-diary as well as CRF, the alternative will be the study-completion/discontinuation date from the Discontinuation form for safety analysis. Subjects lost to follow-up with no information on dosing on e-diary will be excluded from safety analysis.

The statistical evaluation will be performed using SAS version 9.4 or higher.

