4 ANALYSIS POPULATIONS

The following analysis populations will be defined for this study. Subjects' inclusion in or exclusion from these analysis populations will be finalized prior to study unblinding

Randomized population	All randomized subjects. Subjects will be evaluated by the drug to which they are randomized.
Safety population	All randomized subjects who use at least one dose of study drug, regardless of whether or not they undergo any study assessments. Subjects will be evaluated by the drug they use, not by the drug to which they are randomized, when data indicate a difference.
ITT population	All randomized subjects who use at least one dose of study drug and have any post-dose headache severity or symptom assessments. Subjects are evaluated by the drug to which they are randomized.
mITT population	All ITT subjects who treat a migraine attack within four hours of onset. Subjects will be evaluated by the drug to which they are randomized. The mITT population is the primary analysis population.
PP population	All mITT subjects will be considered per protocol (PP) if they do not have major protocol deviations, enumerated below, which might impact the assessment of efficacy. Subjects will be evaluated by the drug to which they are randomized.

Safety-2nd Dose population	All randomized subjects who were considered in the safety population after the first dose and use a second dose of study drug, regardless of whether or not they undergo any study assessments. Subjects will be evaluated by the drug they use, not by the drug to which they are randomized.
ITT-2nd Dose population	All randomized subjects who were considered ITT after the first dose and use a second dose of study drug and have any post-dose headache severity or symptom assessments. Subjects will be evaluated by the drug to which they are randomized.

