1. Retroactive dose entry. If a subject enters the time of a dose retroactively, rather than at the time of taking the dose, the recorded time, and potentially date, of the second dose may be before some or all of the scheduled times of assessments that would otherwise have appeared to be associated with the first dose. In those cases, the apparent first-dose assessments after the recorded time of the second dose, and the second-dose assessments at times calculated from the retroactively entered dosing time will not be included in efficacy analyses.
2. Reports intention to take second dose, without confirmation. Subjects report their intention to take a second dose but may not *confirm* having done so in e-diary. Even if indications of taking second dose are observed in e-diary data, until the entry shows confirmation of second dose times, the e-diary will not have a confirmed second-dose time from which to calculate post-dose assessment times after that second dose, and it will not switch to second-dose mode. In this state, second-dose assessments will be missing. Additionally e-diary continues to collect first dose data although the subject may have taken second dose. Even if use of a second dose is recorded on the on CRF, the related second-dose assessments may not be available in the e-diary because the e-diary is not working in second-dose mode; hence, the exploratory endpoints for second dose will not

be available at those analysis times. Additionally, first dose assessments collected after this time will be considered unscheduled.

3. Multiple reports of a migraine - complicated by aura. If a subject reports a migraine, but does not indicate taking first dose at a specific time due to presence of aura, the efficacy and exploratory analysis endpoints for first and second dose will be summarized for the migraine, which has the reference for most recent available treated migraine data at analysis time points.
4. Missing first dose dates and associated assessments in e-diary. If the first dose is reported taken in the CRF with the appropriate date entered in CRF but the subject did not complete the e-diary for assessments, then the date of first dose and associated assessments will be missing in e-diary data. These subjects (e.g. lost to follow-up) will not be included in appropriate populations of efficacy analysis.

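### For lost-to-follow-up subjects whose dose is confirmed only in the CRF, the closing exclusion in SAP Section 5 contradicts the Safety population definition and the CRF fallback in the same paragraph

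*SAP*

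**What the plan says.** SAP Section 4 defines the Safety population as "All randomized subjects who use at least one dose of study drug, regardless of whether or not they undergo any study assessments". Protocol Section 10.3.1 has the same definition. Neither makes membership depend on where the dose was recorded or on whether the subject was later followed up.

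SAP Section 5 uses the e-diary as the first source of dosing dates and the CRF as the backup. Where Scenarios 4, 5 or 7 of Section 5.4 leave the diary dates missing, CRF alternatives are "used for first and second dose dates for safety analysis if there is a confirmation of dosing in the CRF". Where neither source holds a first-dose date but the "CRF has a confirmation of first dose, the eligibility-confirmation date will be used as the first alternative for safety analyses", and the randomization date is next in line. Section 5 also takes the safety baseline from the first recorded dose in either source. SAP Section 12.1 sets a treatment-emergence window for subjects whose dosing date is in the CRF only.

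The paragraph in Section 5 that contains these fallback rules closes with: "Subjects lost to follow-up with no information on dosing on e-diary will be excluded from safety analysis".

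Scenario 4 of SAP Section 5.4 opens "If the first dose is reported taken in the CRF with the appropriate date entered in CRF but the subject did not complete" the diary, and concludes: "These subjects (e.g. lost to follow-up) will not be included in appropriate populations of efficacy analysis". It mentions efficacy populations only.

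SAP Section 5.1, which lists changes from the protocol's planned analysis, does not mention an exclusion from safety.

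**The concern.** A lost subject with an empty diary and a CRF-confirmed dose meets the definition in Section 4 and qualifies for the CRF fallback, yet is removed by the closing sentence. A programmer who filters on the diary and one who follows Section 4 would build different safety tables from the same data.

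The exclusion acts after dosing. Protocol Section 10 bases all safety analyses on the Safety population, so an adverse event recorded for such a subject would leave the by-arm tables. The Safety-2nd Dose population would be affected as well, since it draws on subjects already in the Safety population after the first dose.

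Protocol Section 4.2 reports treatment-emergent events in Phase 2 in 22% of placebo subjects and in 65%, 73% and 86% at 50, 100 and 200 mg. With tolerability that differs this much between arms, an exclusion applied after dosing could fall unevenly across them. Whether it would is not known.

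**Working it through.** No arithmetic applies. The plan gives no figure for this group, and the question is one of population membership. The check sets the rules side by side for subjects with **no dosing entry in the e-diary**.

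| Case | SAP 4 and protocol 10.3.1 | CRF fallback (SAP 5) and TEAE window (SAP 12.1) | Closing sentence of SAP 5 | Result |
|---|---|---|---|---|
| (a) CRF confirms dose; not lost | In | In | Does not apply | Kept, no conflict |
| (b) CRF confirms dose; lost | In | In | Out | Contradiction |
| (c) No CRF evidence of dose; lost | No evidence that the definition is met | Does not apply | Out | Excluded, no visible conflict |

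Only case (b) is in dispute. Three further checks bear on it.

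1. **Does the plan expect case (b)?** Yes. Scenario 4 describes a dose reported in the CRF with an uncompleted diary, and gives loss to follow-up as its example. It removes these subjects from efficacy only. Section 5 names the same scenario among those to which the CRF safety fallback applies. One sentence of Section 5 therefore keeps these subjects and another removes them.

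2. **How could the CRF show a dose in a subject who misses Visit 2?** SAP Section 5 says that CRF dosing dates and times are normally taken at that visit, so this route is usually closed. Others exist. Under protocol Sections 5.6.1 and 9.2.1 subjects are asked every day how they feel, and an unwell answer prompts the site to call and assess the event. Under protocol Section 9.3 SAEs go into the eCRF within 24 hours of the site learning of them. SAP Section 5 says the diary enters migraine mode only if the subject reports taking the first dose. A subject could therefore dose without logging it, describe an event to the site, and later be lost. The disposition table in SAP Section 6 also has a line for subjects who were treated but did not return for Visit 2, though it does not separate them by source of dosing record.

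3. **Is the exclusion a declared change?** No. Section 5.1 is silent, so nothing indicates that it was meant to override the definition in Section 4.

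**The case against.** The best defence is that the sentence closes a cascade: diary date, then CRF date, then CRF confirmation without a date, then nothing. On that reading it covers only lost subjects for whom no source shows a dose. Visit 2 is the only planned visit after dosing, and lost subjects are by definition those who fail to appear, so most of them will have no CRF dosing report. Leaving them out does not conflict with a definition that requires a dose to have been used.

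This is plausible and may be what was intended, but the sentence does not say it. It names the e-diary and omits the CRF, although the CRF is named throughout the rest of the paragraph. On the benign reading it adds little, because subjects with no recorded dose already fall outside Section 4.

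Two other points on that side stand. Population membership is finalized before unblinding, so the exclusion cannot be chosen with knowledge of treatment. SAP Section 12 also calls for listings of all safety endpoints, so a reported SAE would probably remain visible there even if it left the tables.

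A reader might infer that any subject whose dose is recorded only in the CRF drops out of the safety tables. The documents do not support that: the fallback in Section 5 and the window in Section 12.1 keep such subjects unless they are also lost to follow-up.

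**Conclusion.** The sentence is wrong as written, for one narrow group: lost to follow-up, no dosing entry in the e-diary, and a dose confirmed in the CRF. For these subjects it contradicts the Safety population definition in both documents, the CRF fallback in its own paragraph, and the CRF-only window in SAP Section 12.1.

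The documents give no count. The number is probably small, for the Visit 2 reason above, but Scenario 4 shows that the plan does not treat it as zero. A reader might try to size the group from the gap between 742 randomized and 570 completing per arm. That gap cannot be used, because it includes subjects who never treated an attack and randomization failures, who never dosed. Nor do the documents support a numerical effect on adverse event or SAE rates, or a claim that these subjects were lost because of an adverse event.

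The conclusion rests on the literal wording and needs no assumption about how many subjects are affected. The change is worth making because the rule can remove a dosed subject's events from the tables and because the correction is simple.

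**What to change.** Replace the closing sentence of that paragraph in SAP Section 5 with wording to this effect:

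> A subject lost to follow-up is left out of the safety analysis only if neither the e-diary nor the CRF, including its AE and SAE pages, contains evidence that study drug was taken. A lost subject with such evidence in either source belongs to the Safety population, and the substitute-date rules of this section apply.

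It should be explicit that dosing evidence on an AE or SAE page counts as CRF confirmation, so that the existing date rules can be used. If the narrower exclusion was in fact intended, it should instead be listed and justified in SAP Section 5.1, and the definition in Section 4 changed to match.

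The cost is one sentence. No new data, assessments or analyses are needed. It should be done before population membership is finalized, which Section 4 places ahead of unblinding.

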5.1 Changes and Clarifications from the Planned Analysis

The protocol detailed mITT-2nd Dose and PP-2nd Dose populations. However, the second dose

analyses are all exploratory, and the decision was made to run all exploratory analyses on the ITT and ITT-2nd Dose populations. The mITT-2nd Dose and PP-2nd Dose populations were, therefore, removed.

The protocol stated that statistical testing would be performed to compare demographic data between treatment groups. It was decided that this testing was unnecessary due to the randomization of the study, and these statistical tests were removed from the analysis.

The analyses of the primary efficacy measure and other related measures described in the protocol were limited to headaches that were of moderate or severe intensity at the time of dosing. In keeping with subsequent input to CoLucid from the Food & Drug Administration (FDA), the efficacy endpoints will take into account headaches that were of mild intensity at the time of treatment.

The protocol stated that logistic regression would be used to model efficacy endpoints, but did not detail what method was to be used for non-binary categorical endpoints. The addition of the Cochran-Mantel-Haenszel test is detailed in the relevant sections below to test these endpoints.

Although the protocol did not specify this, it was decided that the exploratory MBS analyses would be repeated separately for each chosen most bothersome symptom (nausea, phonophobia or photophobia). Additionally, a time to MBS-free analysis was added for all MBS endpoints.

The protocol does not mention an additional subgroup analysis but subgroup analysis described in Section 11.8 will be provided.

5.2 Analysis of First and Second Doses

Any analyses based on first dose will only include data observed up to the time of dosing with a second dose. These summaries will be presented based on the first dose taken. The exception to this is the primary and secondary endpoints at the 2-hour time point; if a second dose is taken before the 2-hour time point, the subject will still be included in the summary at 2 hours and will be analysed as having not achieved headache pain-free or MBS-free status at 2 hours.

Any analyses based on the second dose will only include data observed on or after the time of dosing with a second dose. These summaries will be presented by treatment sequence, listed in Section 2.3. Analyses based on the second dose will be done for both the rescue and recurrence subpopulations.

